4.7.1.1 Overall exposure

The exposure information will be assessed by the following variable(s):

- Duration of IMP exposure (in weeks) is defined as (Last day of exposure – first day of exposure +1)/7.

4.7.2 Adverse events

All AEs will be collected from the signing of the ICF until the follow-up visit.

General common rules for adverse events

All adverse events (AEs) will be coded to a lower-level term (LLT), preferred term (PT), high-level term (HLT), high-level group term (HLGT), and associated primary system organ class (SOC) using the Medical Dictionary for Regulatory Activities (MedDRA) version currently in effect at Sanofi at the time of database lock.

The AEs (which are recorded on the AE eCRF page, including hypoglycemia events qualifying as AEs) will be categorized as:

- Pre-treatment AEs: AEs that developed, worsened or became serious during the pre-treatment period, defined as the time from the signed informed consent date up to the first administration of the IMP.
- Treatment-emergent adverse events (TEAE)s: AEs that developed, worsened or became serious during the treatment-emergent period defined as the time from the first administration of the IMP (on Day 1) to the last administration of the IMP + 3 days.
- Post-treatment AEs: AEs that developed, worsened or became serious during the post-treatment period defined as the time starting 1 day after the end of the TEAE period up to the end of the study follow-up (2 weeks after the end of treatment period)

Similarly, the deaths will be analyzed in the pre-treatment, treatment-emergent and post-treatment periods.

Pre-treatment safety data will be analyzed using the Screening Analysis Set. Treatment-emergent and post-treatment safety data will be analyzed using the Safety Analysis Set.

The primary focus of AE reporting will be on TEAEs, and AESIs. Pre-treatment and post-treatment AEs will be described separately.

An AE with incomplete or missing date/time of onset (occurrence, worsening or becoming serious) will be classified as a TEAE unless there is definitive information to determine it is a pre-treatment or a post-treatment AE.

If the assessment of the relationship to IMP is missing for an AE, the AE will be assumed to be related to IMP within summary tables. If the severity is missing for one of the treatment-emergent occurrences of an AE, the severity will be imputed with the maximal severity of the other occurrences within the PT. If the severity is missing for all the occurrences, the severity will be left as missing.

Multiple occurrences of the same event in the same participant will be counted only once in the tables within a treatment phase.

An overdose (accidental or intentional) with the IMP is an event suspected by the Investigator or spontaneously notified by the participant and defined as at least twice the intended dose within the intended therapeutic interval (planned treatment period), adjusted according to the tested drug. Cases of symptomatic overdoses will constitute AESIs and will be listed as such.

The AE tables will be sorted as indicated in [Table 5](#).

Table 5 - Sorting of AE tables

AE presentation	Sorting rules
SOC, HLG, HLT and PT	By the internationally agreed SOC order and by alphabetic order of HLGs, HLTs and PTs.
SOC and PT	By the internationally agreed SOC order and decreasing frequency of PTs ^{a, b}

^a Sorting will be based on the mg dose intervention group/overall incidence.

^b Within each table the sorting will be by the internationally agreed SOC order and decreasing frequency of PTs; in case of tie for PT, the sorting will be alphabetical.

Analysis of all AEs

The overview of TEAE with the details below will be generated (number and percentage of participants) in a table:

- Any TEAE
- Any treatment emergent SAE
- Any treatment emergent AESI
 - Pregnancy.
 - Symptomatic overdose.
 - Increase in ALT (>3 × ULN).
- TEAE leading to death (death as an outcome of the AE as reported in the AE page)
- Any TEAE leading to temporary IMP discontinuation.
- Any TEAE leading to permanent IMP discontinuation

- Any treatment-related TEAE
- Any TEAE leading to study discontinuation

The overview summary for TEAEs will be provided on the safety set and will be repeated on the subgroup of safety participants according to trial impact (disruption) due to the COVID-19 pandemic.

Individual listings (AEs, SAEs, AEs leading to death, TEAEs leading to permanent IMP discontinuation, AESI, AEs for Treated and not enrolled participants) will be provided to support the summary tables based on the safety set.

A listing of all participants who died during the study will be provided.

The AE summaries of [Table 6](#) will be generated with number (%) of participants experiencing at least one event.

Table 6 - Analyses of adverse events

Type of AE	MedDRA levels
All TEAE	Primary SOC, HGLT, HLT and PT
Common TEAE (≥5%)	Primary SOC and PT
TEAE related to IMP	Primary SOC, and PT
TEAE by maximal severity	Primary SOC and PT
Treatment emergent SAE	Primary SOC and PT
TEAE leading to study discontinuation	Primary SOC and PT
TEAE leading to permanent discontinuation of IMP	Primary SOC and PT
TEAE leading to death	Primary SOC and PT
Pre-treatment AE	Overview ^a Primary SOC and PT
Post-treatment AE	Overview ^a Primary SOC and PT
Post-treatment SAE	Primary SOC and PT

^a Will include the following AE categories: any AEs, any serious AEs, any, any AEs leading to death, any AEs leading to permanent IMP discontinuation and be repeated for participants impacted by COVID-19

Analysis of adverse events of special interest (AESIs)

An adverse event of special interest (AESI) is an AE (serious or nonserious) of scientific and medical concern specific to the Sponsor’s product or program, for which ongoing monitoring and immediate notification by the Investigator to the Sponsor is required. Such events may require further investigation in order to characterize and understand them. Adverse events of special

interest may be added, modified, or removed during a study by protocol amendment. All AESIs will be reported to the Sponsor in the same timeframe as SAEs (within 24 hours).

Adverse events of special interest (AESIs) are defined by the protocol and will be documented in eCRF:

- Pregnancy of a female participant enrolled in the study as well as pregnancy occurring in a female partner of a male participant enrolled in the study with IMP/NIMP.
- Symptomatic overdose (serious or nonserious) with IMP/NIMP.
- Increase in ALT (>3 × ULN).

Adverse events of special interest (AESIs) will be selected for analyses as indicated in [Table 7](#). The number (%) of participants experiencing at least one event will be provided for each event of interest. Tables will be sorted as indicated in [Table 5](#).

Table 7 - Selections for AESIs

AESIs	Selection
Symptomatic overdose	eCRF specific tick box on the AE page
ALT Increase	eCRF specific tick box on the AE page
Pregnancy	eCRF specific tick box on the AE page

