4.4.3 Handling of Withdrawals

Participants are free to withdraw from the study or study treatment at any time upon request. Their participation in the study may be stopped at any time at the discretion of the investigator or at the request of the sponsor.

If the participant withdraws consent for disclosure of future information, the sponsor may retain and continue to use any data collected before such a withdrawal of consent.

If a participant withdraws from the study, they may request destruction of any samples taken and not tested, and the investigator must document this in the site study records.

Participants who discontinue study treatment or active participation in the study will no longer receive study drug. When a participant withdraws from the study, the reason(s) for withdrawal shall be recorded by the investigator on the relevant page of the eCRF.

A participant may withdraw from the study or study treatment under the circumstances (including, but not limited to) listed below:

- The participant intends to become pregnant.
- The participant may be withdrawn at the discretion of the investigator due to noncompliance or due to a safety concern.
- The participant will be withdrawn if starting any drugs that interfere with glucose metabolism (eg, steroid doses equivalent to prednisone ≥5 mg/day).
- The participant may be withdrawn if diagnosed with acute pancreatitis (defined as meeting 2 of the following 3 rules: typical abdominal pain; amylase/lipase >3 × ULN; and/or characteristic ultrasound, computed tomography, or magnetic resonance imaging findings).
- If the fasting or the mean SMPG value during 3 consecutive days is >300 mg/dL, the investigator will schedule an unplanned visit as soon as possible to obtain confirmatory FPG and investigate the cause. If no apparent or intercurrent cause is detected, the participant may be withdrawn.
- The participant has recurrent severe hypoglycemia or recurrent nocturnal hypoglycemia during the treatment period that poses a potential risk to the participant, as judged by the investigator.
- The participant is unable to comply with the study protocol, at the investigator's discretion.

Whenever possible, all participants who discontinue study treatment or withdraw from the study prematurely will undergo all end-of-study and follow-up assessments. Participants who fail to return for final assessments will be contacted by the site in an attempt to have them comply with the protocol.

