4.1 GENERAL CONSIDERATIONS

In general, continuous data will be summarized using the number of observations available, mean, standard deviation (SD), quartile ranges, median, minimum, and maximum.

All mean, Q1, Q3 and median values will be formatted to one more decimal place than the measured value. SD values will be formatted to two more decimal places than the measured value. Minimum and maximum will be formatted to the same number of decimal places as the measured value.

Unless otherwise specified below, all confidence intervals (CI) will be two-sided at the 95% confidence level and displayed to the same level of precision as the statistic they relate to. If an estimate or a CI is not estimable, it will be presented as 'NE'. If neither an estimate, nor its CI are estimable, it will be presented as simply 'NE', not displaying 'NE' twice.

The p-values will be two-sided and will be rounded to three decimal places. If a p-value is less than 0.001 it will be reported as '<0.001'. If a p-value is greater than 0.999 it will be reported as '>0.999'.

Categorical data will be summarized using the count and percentage of participants. When count data are presented, the percentage will be suppressed when the count is zero in order to draw attention to the non-zero counts. A row denoted 'Missing' will be included in count tabulations for demographics, baseline characteristics and compliance to account for missing values. No percentages will be displayed on the 'Missing' rows and the percentages on the other rows will be based on the number of non-missing observations. Unless otherwise specified, the denominator for all other percentages will be the number of participants in that treatment within the specific analysis set of interest. All percentages will be rounded to one decimal place. The number and percentage of responses will be presented in the form xx (xx.x), where the percentage is in the parentheses. When the numerator is equal to the denominator, the percentage should be presented as (100) instead of (100.0), unless otherwise specified.

The baseline value is defined as the last available value before the first injection of Soliqua 100/33. Participants enrolled but not treated will have a last available measurement following enrollment.

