If multiple valid values of a variable (efficacy or safety) exist within a same day (and the recorded times of measurement do not identify which of them is the last assessment), the value measured during the scheduled visit will be used as Baseline in the analysis. If none of those values were assessed during a scheduled visit, then all these measurements will be used for the analysis and the average will be calculated to derive the baseline value.

In general, descriptive statistics of quantitative efficacy and safety parameters (result and change from baseline) by scheduled visits will be provided on observed cases (OC; ie, inclusion of only participants having non-missing assessments at a specific visit).

Baseline safety and baseline efficacy results are presented in the safety and efficacy analyses, respectively.

All safety analyses will be performed on the safety analysis set.

Statistical analysis will be performed using SAS Enterprise software Version 9.4 or higher.

Observation period

The observation period will be divided into 3 segments:

- The **pre-treatment period** is defined as the period up to first IMP administration. There are two periods within pre-treatment period. A 2-week screening period and a 2-week run-in period.
- The **on-treatment period** (ie, treatment-emergent (TE) period) is defined as the period from the first IMP administration to the last IMP administration during Visit 7 (Week 16).
- The **post-treatment period** is defined as the period from the end of the on-treatment period to the end of the 2-week safety period. (Week 18)

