4.7.4 Additional safety assessments

4.7.4.1 Laboratory variables and vital signs

The following laboratory variables and vital signs will be converted into standard international units and analyzed from screening to week 16 per the schedule of events. Analysis will distinguish

between early end of treatment and week 16 end of treatment. Glucose values will be analyzed using conventional units.

- Hematology:
 - Red blood cells and platelets: erythrocytes, platelet count, leukocytes, hemoglobin, hematocrit
- Clinical chemistry:
 - Metabolism: lipase, amylase
 - Electrolytes: sodium, potassium
 - Renal function: creatinine, uric acid
 - Liver function: alanine aminotransferase, aspartate aminotransferase, alkaline phosphatase, total bilirubin (if >ULN , then the direct and indirect subfractions must be measured)
- Calcitonin
- Urinalysis:
 - Urinalysis for quantitative analysis: pH, ketones, leukocytes, blood/hemoglobin, protein and glucose
- Vital signs: pulse rate, systolic and diastolic blood pressure, weight

Specified in the study protocol, all clinical safety laboratory assessments will be performed by a central laboratory. Additional tests may be performed at a local or central laboratory at any time during the study as determined necessary by the investigator or required by local regulations. If they are used to evaluate an AE (diagnostic, follow-up, outcome), the results must be entered into the eCRF. A urine pregnancy test will be performed at each schedule of event timepoint and treated as an AESI and not reported in the laboratory analysis tables.

Quantitative analyses

Descriptive statistics will be used for results and changes from baseline will be provided for each planned visit, during the on-treatment period. Laboratory values below the lower limit of quantification (LLOQ) will be set to one half of the LLOQ.

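### The ALT >3×ULN event of special interest is counted only from a tick box on the AE page; no count is derived from the central-laboratory ALT values

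*SAP*

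**What the plan says.** SAP 4.7.2 lists three AESIs, one of which is "Increase in ALT (>3 × ULN"). Table 7 of that section gives one selection rule for all three: "eCRF specific tick box on the AE page".

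For laboratory variables, SAP 4.7.4.1 says that they are "analyzed from screening to week 16 per the schedule of events" and that early end of treatment is to be told apart from the Week 16 end of treatment. Its only analysis subsection is quantitative: "Descriptive statistics will be used for results and changes from baseline will be provided for each planned visit, during the on-treatment period". SAP 4.1 gives the content of such summaries for continuous data as the number of observations, "mean, standard deviation (SD), quartile ranges, median, minimum, and maximum". It also sets the period: on-treatment "is defined as the period from the first IMP administration to the last IMP administration during Visit 7 (Week 16").

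SAP 5.4.5 assigns post-baseline laboratory data, unscheduled visits included, to the day windows of Table 8. Where a window holds two visits, it keeps the one nearer the target day.

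**The concern.** An ALT AESI is a number compared with a limit, and the central laboratory supplies that number. Counting it only from a form makes the safety result depend on each site noticing the value, entering an AE and ticking the box. The SAP does not compare that count with the laboratory data. It plans no table of participants above the limit, no shift table and no listing of out-of-range values.

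At stake is the credibility of a small count. In a trial of about 100 participants the expected number of ALT AESIs is likely to be none or very few, so one unreported case is the difference between none and some.

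**Working it through.** The plan states no figure to reproduce here. The check is of text, with a short illustration of scale.

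**1. Is there a laboratory-derived count?** Table 7 uses the tick box. Table 6 counts reported AEs. SAP 4.7.4.1 gives descriptive statistics only. None of them compares ALT values with 3×ULN, so no count is planned. By contrast, SAP 4.7.3 classifies ADA Level 1 and Level 2 hypoglycemia from the recorded glucose measurement. The SAP thus already derives a safety category from a measured value where one exists.

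**2. Would an unreported exceedance show elsewhere?** The schedule of events has clinical chemistry at Visits 1, 3.1 and 7, so Visit 7 is the only planned ALT after the first dose. An exceedance kept for Visit 7 could appear as the maximum. A maximum shows one value, without reference to ULN, and does not say how many participants exceeded the limit.

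**3. When would it not show even as a maximum?**
- *Closest-to-target rule.* Table 8 gives Week 16 as days 103 to 116 with target day 113. Suppose an unscheduled ALT on day 105 is above 3×ULN and the Visit 7 value on day 113 is normal. The distances are |105 − 113| = 8 and |113 − 113| = 0, so the normal value is used. Protocol 6.3.3 asks for clinically significant abnormal values to be repeated, so pairs like this are foreseeable.
- *Last-dose cut-off.* The on-treatment period ends at the last dose. TEAEs, by comparison, run "to the last administration of the IMP + 3 days". Protocol 4.4.1.1 allows end-of-treatment procedures as soon as possible after the decision to stop, so a sample drawn after the last dose is possible.
- *Planned-visit restriction.* Table 8 would place an early-termination sample on, say, day 40 in Week 8 (days 2 to 60). No chemistry is planned at Week 8.

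**4. Are the statements in SAP 4.7.4.1 consistent?** One sentence separates early end of treatment from Week 16. Another limits the statistics to planned visits on treatment. An early-termination sample taken after the last dose is covered by the first and excluded by the second. The text does not say which governs.

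**5. Scale, under assumed rates.** Take 100 participants (the planned enrolment) as the safety set. The chance of at least one true exceedance is 1 − (1 − p)^100:

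| Assumed rate p | Chance of at least one case |
|---|---|
| 0.5% | 39% |
| 1% | 63% |
| 2% | 87% |

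Protocol 8.7.8 plans 95% confidence intervals for safety proportions. The exact limits are:

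| Counted | 95% CI |
|---|---|
| 0/100 | 0 to 3.6% |
| 1/100 | 0.03 to 5.4% |
| 2/100 | 0.2 to 7.0% |

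For 0/100 the upper limit is 1 − 0.025^(1/100) = 3.6%. One missed participant moves the reported upper limit from 5.4% down to 3.6%. The rates are assumptions; the documents give none.

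**The case against.** The strongest reply is that the protocol already provides a route from the laboratory value to the count. Under Protocol 6.3.3 the investigator must review each laboratory report, and a finding that meets an AESI definition is reportable as an AE. AESIs go to the sponsor within 24 hours, and the sponsor and medical monitor review AEs monthly. An elevation entered as an AE with the box left unticked would still appear in the AE tables by SOC and PT and in the AE listing. All of this stands, and it keeps the point minor. It does not answer the point, because comparing the central-laboratory values with the tick box is how one verifies that the route worked.

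A reader might infer more than the documents support:
- *That the laboratory tables show only means.* They do not; minimum and maximum are planned.
- *That exceedances can appear in no safety table.* This is true only of a value that is both unreported as an AE and dropped by the visit or period rules. The routine Visit 7 sample should fall inside the period, since participants arrive undosed and inject at the site (Protocol 6.2.2 and 6.2.4).
- *That samples from early stoppers are excluded.* SAP 4.7.4.1 intends to show them separately. The fault is an unresolved inconsistency.
- *That early stoppers are the participants most likely to have raised enzymes.* Nothing in the documents says so.
- *That laboratory data must follow the TEAE window of 3 days after the last dose.* The SAP uses different windows for different data, for example 1 day for hypoglycemia and concomitant medication, and no text requires 3 days for laboratory values.
- *That a count for "amylase/lipase >3 × ULN" is also missing.* In Protocol 4.4.3 that limit is part of one of three findings, two of which define acute pancreatitis. It is not an AESI or an analysis threshold, so a count is optional.

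**Conclusion.** The point holds in a limited form. The ALT AESI count rests on a tick box alone, no count above 3×ULN is derived from the laboratory data, and an exceedance that is not reported as an AE is never counted. Under the closest-to-target rule or the last-dose cut-off it may also be absent from the laboratory summaries. SAP 4.7.4.1 needs its two statements on early end of treatment reconciled.

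The number of missed events cannot be estimated from the documents, and with full site compliance it would be zero. The intervals shown assume 100 participants in the safety set. Nothing here rests on the decision tree in Protocol 13.6, whose figure was not available. The matter does not touch the primary analysis. It is a low-cost improvement to the safety reporting.

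**What to change.** In SAP 4.7.2 and 4.7.4.1:

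1. Derive from the laboratory data the n (%) of participants with any ALT above 3×ULN after the first dose. Use all values, including unscheduled, repeat and early-termination samples, without the closest-to-target selection.
2. List these participants with baseline ALT status, and flag values drawn after the last dose. Baseline status matters because exclusion criterion 9 leaves an abnormal screening result to the investigator's judgment.
3. Reconcile the laboratory-derived cases with the tick-box cases and report any difference.
4. State how the on-treatment and planned-visit restriction applies to early end-of-treatment samples, so that it agrees with the sentence that distinguishes them from Week 16.

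The cost is one table, one listing and a few sentences in the SAP, with no new data and no change to study conduct. The ALT count may become slightly less favourable. An amylase and lipase count could be added to the same table if wanted.

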4.7.3 Hypoglycemia events

During the study, participants are to be instructed to document any hypoglycemic episodes in their e-diary. Hypoglycemia will be reported on the specific eCRF page with onset date and time, symptoms and/or signs, the glucose measurement obtained at the time of the event before countermeasures, the collection date and time of glucose measurement, and the treatment of hypoglycemia. Hypoglycemia meeting the definition of an adverse event will be documented, in addition, on the AE form in the eCRF.

The following hypoglycemia events are the categories of interest:

- Any Hypoglycemia Event: Any event recorded in Hypoglycemic Event Information Library eCRF page that has “Yes” as the response to the question “Were any hypoglycemic events experienced”, regardless of the plasma glucose measurements.
- ADA Level 1 Hypoglycemia: A measurable glucose concentration of <70 mg/dL (3.9 mmol/L) but ≥54 mg/dL (3.0 mmol/L) that can alert a person to take action. A blood glucose concentration of 70 mg/dL (3.9 mmol/L) has been recognized as a marker of physiologic hypoglycemia in humans. Recurrent episodes of hypoglycemia lead to increased hypoglycemia unawareness. Therefore, glucose levels <70 mg/dL (3.9 mmol/L) are clinically important, independent of the severity of acute symptoms. The event will be captured if the Glucose Measurement in the Hypoglycemic Event Information Library eCRF page falls within the described blood glucose concentration levels.

- ADA Level 2 Hypoglycemia: A measurable glucose concentration of <54 mg/dL (3.0 mmol/L) that needs immediate action. At approximately 54 mg/dL (3.0 mmol/L), neurogenic and neuroglycopenic hypoglycemia symptoms begin to occur, ultimately leading to brain dysfunction at levels <50 mg/dL (2.8 mmol/L). Neuroglycopenic symptoms, including behavioral changes, visual changes, seizure, and loss of consciousness, are the result of central nervous system neuronal glucose deprivation. The event will be captured if the Glucose Measurement in the Hypoglycemic Event Information Library eCRF page falls within the described blood glucose concentration levels.
- ADA Level 3 Hypoglycemia: A severe event characterized by altered mental and/or physical functioning that requires assistance from another person for recovery due to participant's inability to help themselves. Severe hypoglycemia captures events during which the symptoms associated with hypoglycemia affect a participant such that the participant requires assistance from others. The event will be captured if the Glucose Measurement in the Hypoglycemic Event Information Library eCRF page falls within the described blood glucose concentration levels and if "Required Assistance because subject was not capable of helping self" was selected.
- Documented Hypoglycemia: (<70 mg/dL): a glucose level of <70 mg/dL (or <3.9 mmol/L) (with or without symptoms).
 - Documented Symptomatic Hypoglycemia (<70 mg/ dL): defined as an event during which typical symptoms of hypoglycemia are accompanied by a measured plasma glucose concentration less than 70 mg/dL (3.9 mmol/L). Clinical symptoms that often result from a hypoglycemic episode can include (but not necessarily limited to) increased sweating, nervousness, asthenia/weakness, tremor, dizziness, increased appetite, palpitations, headache, sleep disorder, confusion, seizures, unconsciousness, or coma.
 - Documented Symptomatic Hypoglycemia will be identified in the Hypoglycemic Event Information Library eCRF page in those who indicated "symptoms were present" with a measured plasma glucose value <70 mg/dL (or <3.9 mmol/L)
 - Documented Serious Symptomatic Hypoglycemia: defined as an event where the participant also requires assistance from another person for recovery due to participant's inability to help themselves, i.e., identified in the Hypoglycemic Event Information Library eCRF page, as "Required assistance because subject was not capable of helping self".
 - Documented Non-serious Symptomatic Hypoglycemia: defined as an event where the participant does not require assistance from another person for recovery, i.e., identified in the Hypoglycemic Event Information Library eCRF page, with a "No Assistance" response or "Received Assistance but Subject Was Capable of Helping Self".
 - Documented Asymptomatic Hypoglycemia: asymptomatic hypoglycemia is defined as an event not accompanied by typical symptoms of hypoglycemia but with a measured plasma glucose concentration < 70 mg/dL (or <3.9 mmol/L) i.e., identified in the

Hypoglycemic Event Information Library eCRF page with a “No” response to “Were symptoms present”.

- Symptomatic Hypoglycemia: defined as any symptomatic hypoglycemia recorded on Hypoglycemic Event Information Library eCRF page responding that symptoms were present with the plasma glucose measurements of < 70 mg/dL (or < 3.9 mmol/L).
- Pseudohypoglycemia: defined as any symptomatic hypoglycemia recorded on Hypoglycemic Event Information Library eCRF page responding that symptoms were present with the plasma glucose measurements of ≥ 70 mg/dL (or ≥ 3.9 mmol/L).

Hypoglycemia events categorized by time of day at which the event occurred by ADA levels, will be provided in a table:

- Nocturnal Hypoglycemia Defined by Time of the Day: Any hypoglycemia event that occurs between 00:00 and 05:59, regardless of whether the participant was awake or woke up because of the event.
- Nocturnal Hypoglycemia Defined by Sleep Status: Any hypoglycemia event that wakes the participant from sleep between bedtime and rising in the morning, i.e., before the morning assessment of fasting prebreakfast SMPG and before any insulin injection. The participant wakes up because of the event.
- Daytime Hypoglycemia Defined by Time of the Day: Any hypoglycemia event that occurs between 06:00 and 23:59.
- Daytime Hypoglycemia Defined by Awake Status: Any hypoglycemia event that occurs between the participant waking up and going to sleep.

Hypoglycemia observation periods

- Pre-treatment hypoglycemia events are events that developed or worsened or became serious from the signed informed consent date up to first administration of the IMP.
- Treatment-emergent hypoglycemia events are those that developed or worsened or became serious during the on-treatment period arising from the time of the first IMP administration (on Day 1) up to 1 day after the last IMP injection.
- Post-treatment hypoglycemia events are events that developed or worsened or became serious during the post-treatment period arising 1 day after the end of the TEAE period up to the end of the study follow-up (2 weeks after the end of treatment period)

Descriptive analysis will summarize hypoglycemia events in a table (repeat for subgroups [i.e., OAD only at baseline, OAD plus GLP-1 RA at baseline, ≥ 65 years of age, < 65 years of age]):

- Overall number and percentage of participants with at least 1 hypoglycemia event (for overall and each observation period) and number of hypoglycemic events (for overall and each observation period)
- Number and percentage of participants with at least 1 hypoglycemia event and number of hypoglycemic events, by ADA classification levels

- Number and percentage of participants with at least 1 hypoglycemia event and number of hypoglycemic events, by observation periods
- Documented Hypoglycemia
 - Documented symptomatic hypoglycemia
 - Documented serious symptomatic hypoglycemia
 - Documented non-serious symptomatic hypoglycemia
 - Asymptomatic Hypoglycemia
- Symptomatic Hypoglycemia
- Pseudohypoglycemia
- Nocturnal Hypoglycemia Defined by Time of the Day, overall and by ADA levels
- Nocturnal Hypoglycemia Defined by Sleep Status, overall and by ADA levels
- Daytime Hypoglycemia Defined by Time of the Day: overall and by ADA levels
- Daytime Hypoglycemia Defined by Awake Status, overall and by ADA levels

In addition, rate of on-treatment symptomatic hypoglycemic events (Overall, and by time of day per ADA levels) will be summarized in a table whereas

Hypoglycemic events rate per participant year = Number with hypoglycemic events/Total Person Years

If there are multiple events from an individual participant, all events will be counted.

where Total PY is calculated as below:

Observation period	Total Person Years	Time to event (days)	Censoring time (days)
On-treatment	(cumulative total time to event date for participants with event + cumulative total of censoring time for participants without event)	date of event -first dose date +1	(last dose date+1) -first dose date +1

Participants with symptomatic hypoglycemia events, and participants with severe hypoglycemia events will be displayed in listings. A figure will be provided showing the time to the first severe or documented ADA Level 3 symptomatic hypoglycemia during on-treatment period.

